### ***Measurement of Outcomes***

Table 1 describes all outcomes. The primary feasibility outcomes that will be measured are recruitment, retention, data completion, and participant satisfaction. We will consider a larger trial feasible if recruitment rates are  $\geq 50\%$ , retention rates are  $\geq 80\%$ , and the data completion rate for all secondary clinical outcomes is  $\geq 80\%$ . Participant satisfaction with different aspects of the study will be measured at the exit questionnaire using a Likert scale and semi-structured qualitative free-text responses.

Secondary outcomes will include BMI change from baseline to 6-months. Interventions are more successful if longer than 4 months in duration.(36) All study participants will have one in-person visit with the research assistant at the start of the study where baseline weight and height will be measured using standardized methods with calibrated study instruments. Participants (both intervention and control) will then receive a Fitbit activity tracker to wear for the duration of the study. Study participants will be asked to visit the

study office once a month to conduct a self weigh-in using a Fitbit electronic ‘smart’ scale (e-scale). They will be asked to weigh themselves monthly and reminders will be sent by email or text message. E-scales are feasible and valid for research conducted remotely and participant adherence to home weigh-ins is high(37–39), as part of this feasibility study we will assess the adherence to self weigh-ins when the scale is located in a private study office. Other secondary outcomes will include nutrition risk, physical activity (measured as 24-hour movement, including sedentary time and sleep), and mental health collected using online questionnaires at baseline and every 2 months. Nutrition risk will be measured using the National Cancer Institute's Dietary Screener Questionnaire (DSQ). The DSQ measures the frequency of intake of selected foods that are known to affect risk of cancer and obesity, including fruits, vegetables, whole grains, and sugary drinks. The DSQ has good validity compared to 24-hour recalls.(40) Self-reported physical activity, sedentary time, recreational screen time and sleep will be measured to describe adherence to recommended 24-hour movement guidelines using questionnaires previously used in young adults(41), including the International Physical Activity Questionnaire (IPAQ)(42), and International Sedentary Assessment Tool (ISAT).(43) The Insomnia Severity Index will also be included as a measure of perceived sleep quality.(44) Mental health is an important upstream determinant of health behaviours and is highly associated with obesity risk. We will measure depressive symptoms, anxiety and health-related quality of Life using the following validated tools: Centre for Epidemiologic Studies Depression Measure -10 (CESD-10)(45), Generalized Anxiety Disorder -7 (GAD-7)(46), and Euroqol-5D-5L (EQ-5D-5L).(47) We anticipate that some youth may also raise issues related to alcohol or substance use in the interviews, thus we have included questions that ask about alcohol, smoking, cannabis and medication use in the questionnaires. A single-item measure of body satisfaction is included in the study to evaluate any changes over the course of the study.(48) A validated two-item food insecurity screen is also included.(49)

For objective 3, we will evaluate whether feasibility and other secondary outcomes differed for participants who were identified as high versus low risk using existing obesity risk stratification tools. Three validated risk stratification tools will be applied to the data to explore these differences.(28–30) The Edmonton

Obesity Staging System will also be used.(50) The required variables for each of the risk tools will be collected from the baseline questionnaire (e.g., parent obesity, history of child obesity, alcohol, smoking, medical history). Feasibility data to inform costing and economic analyses for a larger scale trial will be collected. In addition to the EQ-5D-5L, self-reported healthcare use, and time missed from school/work will be collected on the surveys. For this pilot study a descriptive cost analysis will be conducted.

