## ABSTRACT

**Background:** Obesity is a chronic disease and is an established risk factor for other chronic diseases and mortality. Young adulthood is a period when people may be highly amenable to healthy behaviour change, develop lifelong healthy behaviours, and when primary prevention of obesity may be most feasible. Interventions in early adulthood have the potential for primary or primordial prevention (i.e., preventing risk factors before disease onset). The primary objective of this study is to determine the feasibility of a 6-month behavioural and educational intervention to promote healthy behaviours for obesity prevention among young adults.

**Methods:** This is the study protocol for a pilot randomized controlled trial. Young adults (age 18-29) attending McMaster University, Hamilton, Canada, will be recruited and randomized to either the intervention or control. The intervention will include individual motivational interviewing sessions (online or in-person) with a trained interviewer plus educational materials (based on Canada's food guide and physical activity recommendations). The control group will receive educational materials only. The primary feasibility outcomes that will be evaluated as part of this pilot study include enrollment, retention ( $\geq 80\%$ ), data completion ( $\geq 80\%$  of weights measured, and surveys completed), and participant satisfaction. Secondary clinical outcomes will include body mass index (BMI) change from baseline to 6-months, physical activity, nutrition risk, health-related quality of life mental health and economic outcomes. Outcomes will be measured remotely using 'smart' electronic scales, activity trackers, and online questionnaires at baseline and every 2 months. Risk stratification will be applied at baseline to identify participants at high risk of obesity (e.g., due to family or personal history). Exit questionnaires will collect data on how participants felt about the study and cost analysis will be conducted.

**Discussion:** Our pilot randomized controlled trial will evaluate the feasibility of an obesity prevention intervention in early adulthood and will inform future larger studies for obesity prevention. The results of this

study have the potential to directly contribute to the primary prevention of several types of cancer by testing an intervention that could be scalable to public health, post-secondary education, or primary care settings.

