### ***Timing of Visits, Intervention and Control Groups***

An overview of the study design is provided in Figure 1. The first visit will occur in-person with a research assistant to obtain consent, collect baseline measures, provide participants with the study materials/equipment, and build a relationship with the study participants. For all subsequent visits, participants will have the option of in-person or virtual sessions.

The intervention will include motivational interviewing sessions with a trained research assistant/interviewer plus educational material. The motivational interviewing sessions will occur at baseline and once a month (7 visits in total). For this feasibility study, *a priori* criteria for the discontinuation or modification of the allocated intervention are not available.

The research assistant will receive training in motivational interviewing. Intervention fidelity (adherence to the principles of MI) will be assessed using recorded training interviews and established rating scales with continuing training as needed.(33) For training purposes, mock interviews conducted between members of the research team will be recorded and evaluated. Interviews with study participants will not be recorded.

The control group will receive educational material only. The same educational material will be provided to both the intervention and control group and will consist of evidence-based recommendations based on Canada's food guide(34) and Canadian 24-hour movement guidelines.(35) The SPIRIT schedule of enrolment, interventions, and assessments for this study is provided in Figure 2.

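### The abstract says outcomes are measured remotely, but follow-up weights depend on monthly visits to a study-office scale with no fallback described, so weights may be missing unequally by arm and session mode

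*Combined protocol and SAP*

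**What the plan says.** The abstract states: "Outcomes will be measured remotely using 'smart' electronic scales, activity trackers, and online questionnaires at baseline and every 2 months". Measurement of Outcomes describes a different procedure. Baseline height and weight are measured by staff. Participants in both arms are then asked to visit the study office "once a month to conduct a self weigh-in using a Fitbit electronic" smart scale, with email or text reminders. That section supports the approach with evidence that "participant adherence to home weigh-ins is high", and then says that "we will assess the adherence to self weigh-ins when the scale is located in a private study office". Table 1 specifies WiFi-enabled scales for BMI change but not where they stand. Home WiFi is an inclusion criterion, although the text describes no home scale.

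Timing of Visits, Intervention and Control Groups says, after the in-person first visit: "For all subsequent visits, participants will have the option of in-person or virtual sessions". For the intervention arm, "The motivational interviewing sessions will occur at baseline and once a month (7 visits in total"). For the comparator, "The control group will receive educational material only".

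Under Data collection and management, a $30 gift card accompanies each completed survey. The surveys are online, with follow-up at 2, 4 and 6 months. The abstract counts weights measured within the data-completion outcome (at least 80%). Neither the abstract, Measurement of Outcomes nor Table 1 says whether that threshold applies overall or by arm. Data Analysis names multiple imputation for missing data without giving a model or a sensitivity analysis.

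**The concern.** A reader cannot tell from the plan how someone who does not come to the office is to be weighed, and no substitute weight is described for that person.

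The effort of being weighed is also not the same for everyone. An intervention participant who attends sessions in person is already on site each month. A control participant, or an intervention participant who chooses virtual sessions, has to come for the weigh-in alone. Reminders are not limited to one arm, but they do not remove that difference in effort. The gift card rewards an online survey rather than the trip.

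Two things are at stake. Weight completion feeds a primary feasibility outcome, and a single overall rate could look adequate while one arm does poorly. In addition, the 6-month BMI change, whose variability is meant to inform the larger trial, could be observed in differently selected subsets of the two arms.

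**Working it through.** **1. The plan's own figure.** Sample size gives 95% confidence, 80% completion, a 7.5-point margin and 110 participants. With n = z² p(1 − p)/d²: 1.96² × 0.80 × 0.20 / 0.075² = 109.3, rounded up to 110. The figure reproduces and is not disputed. By the same formula the half-width is 1.96 × √(0.16/110) = 7.5 points overall and 1.96 × √(0.16/55) = 10.6 points in one arm of 55.

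**2. What an overall rate can hide.** Allocation is 1:1, so the overall rate is the mean of the two arm rates. The documents give no arm-specific rates, so those below are assumed.

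| Intervention / control | Overall | Expected weights (of 55 / of 55) | Gap |
|---|---|---|---|
| 80% / 80% | 80% | 44.0 / 44.0 | 0 points |
| 85% / 75% | 80% | 46.8 / 41.2 | 10 points |
| 90% / 70% | 80% | 49.5 / 38.5 | 20 points |
| 95% / 65% | 80% | 52.2 / 35.8 | 30 points |

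An overall rate cannot distinguish these rows. The 95% half-width for the difference in completion between arms is about 14 to 15 points throughout. Reporting by arm would therefore show a gap of 20 points clearly and one of 10 points only loosely.

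**3. Effect on BMI change.** Let m be the share unweighed in an arm, and D the mean BMI change in unweighed minus weighed participants. The observed arm mean equals the full mean minus m × D. If D is the same in both arms, complete-case bias in the arm difference (intervention minus control) is D × (m_control − m_intervention).

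Take 90%/70% completion, so m is 0.10 and 0.30, and assume D = 0.3 to 0.5 BMI units:
- Control mean too low by 0.30 × 0.3 = 0.09 to 0.30 × 0.5 = 0.15.
- Intervention mean too low by 0.10 × 0.3 = 0.03 to 0.10 × 0.5 = 0.05.
- Bias in the arm difference: 0.20 × 0.3 = 0.06 to 0.20 × 0.5 = 0.10 BMI units.

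With equal completion the bias is zero under this assumption. With positive D and lower control completion, the bias runs against the intervention.

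**4. Direction of the arm gap.** The only documented source of an arm difference is the monthly sessions, and it operates only through in-person attendance. An intervention participant who goes virtual faces the same separate trip as a control. The more who do so, the smaller the arm gap. Missingness may then rise overall, and session mode becomes the more informative split.

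**The case against.** Office weighing is a declared feasibility question, so poor attendance would be a result of the pilot and not a defect in it. That stands, and the office weigh-in should stay.

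The virtual option can be read as covering counselling only; the Conclusions describe remote visits in terms of motivational interviewing. On that reading it does not contradict a separate weigh-in, and the text asks participants to attend without making it a condition. This also stands. The direct conflict is between the abstract and Measurement of Outcomes; the visits section needs clarifying alongside them.

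All participants are students at the university, and the request and reminders are not limited to one arm. BMI change is secondary and descriptive, without significance testing. The bias above is a complete-case figure, whereas the plan intends multiple imputation. These points limit the consequence. They do not remove it: no imputation model is given, and the intermediate weights come from the same office scale and so may be missing for the same people.

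A reader might infer several stronger things that the documents do not support:
- **That completion is judged on both arms pooled, or that 90%/70% would be rated green.** The threshold is silent on arm, and the traffic-light scheme gives no numeric cut-offs for its colours.
- **That the control-arm shift of 0.09 to 0.15 is the bias.** The intervention arm has missing weights too; the net figure is 0.06 to 0.10.
- **That the bias should be judged against the average Canadian weight gain in the Background.** That is an all-adult average, and the same text says gain is greater in young adults. The comparison would also depend almost wholly on the assumed D.
- **That 80% should be required in each arm.** The sample was sized for the overall rate. At a true 80% in both arms, the binomial chance that 110 participants reach 80% overall (at least 88) is about 56%. The chance that both arms of 55 do so (at least 44 each) is 0.58² = about 34%.

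**Conclusion.** The point holds in limited form. The abstract and Measurement of Outcomes disagree on where weight is taken, and no fallback weight is described in the available text (Figure 1 is not reproduced). Unequal missingness by arm is a reasoned possibility, not a documented rate; its size is unknown, and it shrinks as more intervention participants choose virtual sessions. An overall 80% is compatible with equal arms or with a gap of 20 points or more. The 0.06 to 0.10 BMI units is an illustration resting on three assumptions: 90%/70% completion, a 0.3 to 0.5 unit difference between unweighed and weighed participants that is equal in both arms, and a complete-case analysis. The matter deserves attention because weight completion enters a primary feasibility outcome, the pilot's estimates feed the next sample size, and the remedy is cheap.

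**What to change.** 1. Reconcile the abstract, Timing of Visits and Measurement of Outcomes on where follow-up weight is measured, and state whether the virtual option applies to sessions only.
2. Keep the office weigh-in and the overall 80% threshold. Report weight completion by arm and, in the intervention arm, by session mode, with confidence intervals (about ±10.6 points at 55 per arm if completion is 80%, wider for session-mode subgroups).
3. Add one dated weight item, flagged as self-report or home scale, to the existing 2-, 4- and 6-month online surveys. Use it only as an auxiliary variable in the multiple imputation and in a sensitivity analysis. Do not count it toward office weigh-in adherence.

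The cost is one survey item, some table rows and a few sentences of text, with no extra visit. The small downside is that backup weights are less accurate, so they stay out of the main BMI summary.

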Young adulthood is a period when people may be highly amenable to healthy behaviour change, develop lifelong healthy behaviours, and when the primary or secondary prevention of obesity may be feasible. Interventions in young adults have the potential for primary cancer prevention (i.e., stopping cancer risk factors before they develop). Young adulthood is a time when weight gain may occur rapidly(21) and developing healthy behaviours is critical to maintaining a healthy weight throughout adulthood. On average, Canadian adults gain 0.5 to 1 kg every two years and this is greater among young adults and those with higher BMI.(22) Systematic reviews suggest that students attending post-secondary education may experience greater weight gain.(23,24)

Narrowly defined lifestyle interventions for obesity prevention, such as those addressing only physical activity, have had limited success.(25) The 2020 Obesity Clinical Practice Guidelines recommend moving “*beyond simplistic approaches of “eat less, move more,” and address the root drivers of obesity*”.(11) Yet, there have been relatively few attempts to implement tailored, population-based obesity prevention interventions in young adults. Obesity interventions must be flexible to address the complex causes of obesity and motivational interviewing may be a successful strategy.(25) Motivational interviewing (MI) is defined as “*a collaborative conversation style for strengthening a person’s own motivation and commitment to change*”.(26) Health care professionals have successfully used motivational interviewing for patients to set personalized goals for successful healthy life changes.(27) Motivational interviewing has shown some success for weight loss interventions in young adults,(25) but it has not been widely implemented for obesity prevention. It is unknown whether obesity prevention interventions are more successful among people at highest risk. Several obesity risk stratification tools have been developed and validated that identify young adults who are at greatest risk of obesity later in adulthood.(28–30) The use of these risk prediction tools to identify young adults who may benefit the most from an obesity prevention intervention may improve success and support broader population-level, precision public health or clinical interventions.

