**The primary study objective is:**

1) To determine the feasibility (enrollment, retention, data completion, satisfaction) of a 6-month behavioural and educational intervention to promote healthy behaviours for obesity prevention among young adults.

The **secondary objectives are:**

2) To determine the effects of the 6-month behavioural and educational intervention, compared to an educational intervention only, on change in BMI, health behaviours (nutrition, physical activity and sedentary time), health-related quality of life, and mental health (depression and anxiety).

3) To explore whether obesity risk stratification tools identify young adults who may be more successful in an obesity intervention.

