### ***Data Analysis***

The analysis and reporting of our results will be done according to the CONSORT guidelines.(51) The data analyst will be blinded. Patient screening, randomization, allocation, and follow-up numbers will be illustrated in a flow diagram. Baseline data will be reported in a table for both groups (Intervention and Control) and summarised as means (standard deviation) or median (first quartile, third quartile) for continuous variables and counts (percent) for categorical variables. Data on feasibility outcomes will be measured and compared to pre-determined thresholds for interpretation. The primary analysis will be by intention-to-treat (data from participants will be analyzed according to their allocation irrespective of whether they received that intervention). For these purposes, a complete data set is required. Multiple imputation techniques will be used to manage missing data points. Comparison of groups for secondary outcomes will be reported descriptively for this pilot study. No formal significance testing for comparisons of the secondary clinical outcomes will be made because this is a pilot study with *a priori* sample size determined based on feasibility outcomes only. It is well established that there are sex and gender differences in obesity.(52) Disaggregated data on sex and gender will be reported.

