### ***Sample size***

Our sample size estimation was based on feasibility considerations and calculated using WINPEPI.(53) Using a 95% confidence level, assuming that 80% of the participants will complete the study with a 7.5% margin of error, 110 participants are needed (55 intervention and 55 control). This sample size is not sufficiently powered to make between-group comparisons but will provide accurate data on feasibility and estimates of effect size variability that will inform the sample size calculation of a larger definitive trial.

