## **CONCLUSIONS**

Although it is well recognized that the causes of obesity are complex, many obesity trials have evaluated a narrowly defined “one size fits all” intervention. We will evaluate the feasibility of a tailored intervention delivered through motivational interviewing sessions with a trained research assistant interviewer. This approach will allow participants to set their own behavioural change goals. Further, we are evaluating the feasibility of a targeted or risk stratification approach to an obesity intervention to determine if higher-risk young adults benefit more from the intervention.

This intervention is designed to be flexible to focus on a broad range of health behaviours so study participants can set behavioural change goals related to the behaviours that they think are most important to them. While for some participants, this may focus on traditional, obesity-related risk factors such as diet or physical activity, for other participants this may include behaviours related to sleep, mental health, substance use, or time management. All these behaviours have the potential to either directly or indirectly impact obesity prevention.

Our feasibility trial will inform future larger RCTs for obesity prevention. The results of this study have the potential to directly contribute to the primary prevention of several types of cancer by testing an intervention that could be scalable to public health, post-secondary education, or primary care settings. This study is pragmatic with the option of remote visits for MI. Unlike traditional MI, this format with a trained

interviewer is feasible and the results of the risk stratification objective may inform who would benefit the most from a larger-scale program. This pilot study will provide proof of concept for an intervention that could be expanded to other settings such as public health, post-secondary education, or primary care. If successful, this program could be implemented in university wellness services and may have a profound impact on the primary prevention of an established and highly prevalent chronic disease risk factor.

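### Objective 3 asks whether higher-risk young adults benefit more, but the only analysis written gives no role to arm and, for BMI change, does not isolate differential benefit

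*Combined protocol and SAP*

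**What the plan says.** The list of objectives (end of Background) gives objective 3 as: "To explore whether obesity risk stratification tools identify young adults who may be more successful in an obesity intervention". The Background motivates it by noting that nobody knows whether prevention works better in those at highest risk, and that the tools might find those who stand to gain most. The Conclusions describe the work as evaluating the feasibility of "a targeted or risk stratification approach to an obesity intervention to determine if higher-risk young adults benefit more from the intervention", and add that "the results of the risk stratification objective may inform who would benefit the most from a larger-scale program".

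The analysis is one sentence in Measurement of Outcomes: "we will evaluate whether feasibility and other secondary outcomes differed for participants who were identified as high versus low risk". Three risk tools are to be applied, and the Edmonton staging system is also to be used. No high/low cut is given.

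Data Analysis says "Comparison of groups for secondary outcomes will be reported descriptively for this pilot study" and rules out significance tests on clinical outcomes. Table 1 lists a mean and SD for BMI change. Neither mentions risk group. Sample size adds: "This sample size is not sufficiently powered to make between-group comparisons".

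**The concern.** Whether one group benefits more than another is a question about effect modification: is the intervention-minus-control difference larger at high risk than at low risk? A comparison of high- with low-risk participants is a different quantity, because the two groups may change differently without any intervention. The Background gives reason to expect this. It says of weight gain: "On average, Canadian adults gain 0.5 to 1 kg every two years and this is greater among young adults and those with higher BMI". It also says the tools pick out people at greater later risk.

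If the sentence in Measurement of Outcomes is followed as it stands, a natural difference could be reported as differential benefit, or could hide it. The Conclusions expect these results to help decide whom a larger programme should target. The trial has a control arm, so the right contrast is available from data already being collected.

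**Working it through.** **Plan's own figure.** Sample size assumes 80% completion, a 7.5-point margin and 95% confidence: 1.96² × 0.80 × 0.20 / 0.075² = 109.27, rounded up to 110. It reproduces, and this point does not touch it.

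**What each comparison estimates.** Let mean BMI change be m in low-risk controls and m + g in high-risk controls. Let tL and tH be the intervention effects in the low- and high-risk groups.

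- Arms pooled, half of each risk group in each arm: (m + g + 0.5tH) - (m + 0.5tL) = g + 0.5(tH - tL).
- Intervention arm only: (m + g + tH) - (m + tL) = g + (tH - tL).
- Arm difference at high risk minus arm difference at low risk: tH - tL.

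The pooled form never returns tH - tL. The intervention-arm form does so only if g = 0. Randomization is stratified by sex and BMI, not by risk status, so the pooled form also depends on chance imbalance. With 22 of 110 at high risk (20%, assumed) and 55 per arm, the high-risk share allocated to intervention can stray from 0.5 by about 1.96 × sqrt(22 × 0.25 × 88/109)/22 = 0.19, ignoring the stratification.

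**Illustration (assumed mean BMI changes, kg/m²).**

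| Case | High: control, intervention | Low: control, intervention | Pooled high - low | Intervention arm high - low | tH - tL |
|---|---|---|---|---|---|
| A | 0.6, 0.2 | 0.2, 0.2 | 0.2 | 0.0 | -0.4 |
| B | 0.6, 0.4 | 0.2, 0.0 | 0.4 | 0.4 | 0.0 |
| C | 0.4, 0.0 | 0.2, 0.2 | 0.0 | -0.2 | -0.4 |

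In B the intervention works equally in both groups, yet both simple comparisons show a difference. In A the intervention-arm comparison misses a real extra benefit at high risk. In C the pooled comparison misses it.

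**Scale.** The documents give no g. For scale only, take g = 0.25 kg. This is the upper average gain in the Background, 1 kg per two years, over six months; at an assumed 1.70 m it is 0.25/1.70² = 0.09 BMI units. That figure is an average gain across adults, not a high-low difference, so it is an assumption. With no differential effect both simple comparisons then read +0.25 kg. A true extra benefit of 0.50 kg reads as zero when pooled (0.25 - 0.5 × 0.50), and one of 0.25 kg reads as zero in the intervention arm (0.25 - 0.25). At g = 0 the intervention arm reads tH - tL in full and the pooled form reads half of it.

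**Precision of the right contrast.** The 95% half-width is 1.96 × sqrt(2/nH + 2/nL) SD, with nH and nL counted per arm. The documents give no high-risk share, so 20% to 50% is assumed. The second sample size is 80% of 110 = 88.

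| Analysed | 20% high risk | 30% | 50% |
|---|---|---|---|
| 110 | 0.93 (nH = 11) | 0.82 (16.5) | 0.75 (27.5) |
| 88 | 1.04 (8.8) | 0.91 (13.2) | 0.84 (22) |

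At an assumed SD of 2 to 4 kg this runs from 0.75 × 2 = 1.5 kg to 1.04 × 4 = 4.2 kg. With balanced arms the standard error is twice that of the pooled comparison.

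**The case against.** A reader might infer that the plan commits to a wrong estimator, by pooling the arms or by looking at the intervention arm alone. The documents do not support that. Measurement of Outcomes leaves the role of arm open. Objective 2 is explicitly a comparison with education only, and Data Analysis compares the groups descriptively, so repeating that display within risk group may be what is meant. The two formulae above are consequences of readings that the text permits, not of an analysis that it states.

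The target is also softer than it looks. The formal objective only explores, and speaks of success in an intervention, which could be a prognostic question. The sentence in the Conclusions is introduced as evaluating feasibility. Against that, the Background and Conclusions both speak of benefit, so the effect-modification reading is the natural one.

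Finally, the impact is small. Illustrative shifts of 0.25 to 0.50 kg sit beside half-widths of 1.5 to 4.2 kg, and the plan already disclaims power and tests. All of this stands, and it lowers the priority. It does not remove the mismatch: an imprecise estimate of the right quantity can feed a later trial, whereas a contrast mixed with g cannot be separated afterwards if only the risk-group totals are reported.

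**Conclusion.** The point holds as a gap between question and analysis, for BMI change. No arm-by-risk contrast is written anywhere, and the comparison that is written, taken literally, cannot answer whether higher-risk participants benefit more. The algebra needs no assumed values beyond balanced arms for the pooled form. The sizes rest on assumed values of g, the SD, height and the high-risk share.

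It does not extend to retention, data completion or satisfaction, where comparing risk groups directly is reasonable. Nor should a reader infer that the sample size or the go/no-go decision is at fault: progression rests on the feasibility thresholds, and the pilot could not settle differential benefit under any analysis. This is a cheap improvement of low priority.

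**What to change.** Keep the high-versus-low description for the feasibility outcomes. Add to the objective 3 paragraph in Measurement of Outcomes:

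> *For BMI change, and for each tool with a pre-stated high/low split, results will be shown by arm within risk group, with the intervention-minus-control difference in each risk group and the difference between these with a 95% CI. This is exploratory and no significance test will be made.*

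In the Conclusions, change *determine if* to *explore whether*. Alternatively, if only a description by risk group is wanted, reword the Background, objective 3 and the Conclusions to say so.

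The cost is a few sentences and one small BMI table per tool, with no new data and no conflict with the no-testing rule. A high/low split must be stated for each tool, and the plan should say whether the Edmonton system is to be split. That gives three contrasts, or four with Edmonton. The drawback is small cells: at a 20% high-risk share there are 11 high-risk participants per arm with 110 analysed and about 9 with 88. The results can only generate hypotheses.

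A sentence on imputation is optional. Data Analysis says "Multiple imputation techniques will be used to manage missing data points" but names no model, so there is nothing written to correct. A model without an arm-by-risk term would pull the contrast towards zero. In one simulation (110 participants, 20% high risk, 20% missing completely at random, true contrast -0.50 SD) it averaged -0.39 with an empirical SD of 0.46, against -0.50 with 0.58 when imputing by arm. The root mean squared errors are sqrt(0.11² + 0.46²) = 0.47 and 0.58, so at this size removing the bias costs more in variance than it gains.
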